8.1.5.3 MONTHLY ASSESSMENTS

Participants will be prompted by the CareQOL app to complete a series of self-report surveys at the end of each month (day 30, 60, 90, 120, 150, 180) during the 6-month (180 day) home monitoring period. They will also complete a post-intervention/app feasibility survey at the end of month 6 (day 180). These surveys will be answered directly on the CareQOL app and/or by interview, and should take ~10-15 minutes to complete.

- Study Feasibility: At the 6-month (180 day) assessment only, participants will complete a Study Feasibility survey to assess the experience of the participant with the study methodology and technology, including the CareQOL app, Fitbit®, and the JITAi. Administration time is 5 minutes.

Additionally, participants will update their medical history, medications, therapies, and COVID history and be queried about AEs at the end of month 3 (day 90) and month 6 (day 180).

- Medical History, Medications, Treatments, COVID Questionnaire. Participants will update their medical history and current treatments/management strategies (medication and non-medication – e.g., exercise, mindfulness) and COVID history. Administration time for this assessment is 10 minutes
- Adverse Events. Participants will be asked about any changes in mental or physical health. Administration time is 5 minutes.

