8.1.5.4 FOLLOW-UP ASSESSMENTS

Participants will be prompted by the CareQOL app to complete a series of self-report surveys at +3-months (270 days) and +6-months (360 days) follow-up. As with the monthly surveys, responses will be directly entered into the CareQOL app and/or by interview and should take ~10-15 minutes to complete. Additionally, participants will update their medical history, medications, treatments and COVID history and be queried about AEs at these time points.

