9.4 STATISTICAL ANALYSES

9.4.1 GENERAL APPROACH

Continuous measures will be described using means and standard deviations (or medians and ranges if non-normality is detected), while categorical measures will be summarized with frequencies and percentages.

For inferential tests, a two group t-test with a 0.05 two-sided significance level will be used.

Analyses for primary, secondary, and tertiary endpoints are described individually, below.

The distribution of the data will be examined to ensure that parametric testing is appropriate. In cases where data distributions are not normal, nonparametric tests will be used to analyze the data.

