9.4.2 ANALYSIS OF THE PRIMARY ENDPOINT(S)

Primary Endpoint: TBI-CareQOL Caregiver Strain Short Form (SF). TBI-CareQOL Caregiver Strain assesses perceived feelings of feeling overwhelmed, stressed and “beat-down” related to the care partner role. Self-reported responses are on a Likert scale. This measure is scored on a *T* metric (M = 50; SD = 10). Higher scores indicate more strain.

Self-reported TBI-CareQOL Caregiver Strain (T score) will be used to test the effectiveness of the JITAI. Change from baseline to 6-months post-intervention will be compared between the two arms. Means and standard deviations of the within-person changes will be calculated. In addition, we will model the dependent variable (Caregiver Strain) using linear mixed effect model, where a random intercept will be

NIH Behavioral and Social Intervention Clinical Trial Protocol Template v3.0 - 20180827

included to account for repeated measurements from the same subject. We include in the model the following independent variables: the randomization arm, time and interaction between randomization arm and time, and baseline Caregiver Strain T scores. Key biologic variables such as age, sex, TBI severity, and co-morbidities will be among some of the factors explored as potential confounders. Differences between treatment arms can then be obtained by estimating and testing the corresponding parameters in the linear mixed effect model.

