9.4.3 ANALYSIS OF THE SECONDARY ENDPOINT(S)

Secondary Endpoints:

- PROMIS Anxiety SF. PROMIS Anxiety assesses self-reported feelings of fear, anxiety and hyperarousal. Self-reported responses are on a Likert scale. This measure is scored on a *T* metric (M = 50; SD = 10). Higher scores indicate more anxiety. Administration time for this measure is ~1 minute.
- PROMIS Depression SF. PROMIS Depression assesses self-reported feelings of sadness and worthlessness. Self-reported responses are on a Likert scale. This measure is scored on a *T* metric (M = 50; SD = 10). Higher scores indicate more depression. Administration time for this measure is ~1 minute.

Self-reported PROMIS Anxiety (T score) or PROMIS Depression (T score) will be used to test the effectiveness of the JITAI. Change from baseline to 6-months post-intervention will be compared between the two arms. Means and standard deviations of the within-person changes will be calculated. In addition, we will model the dependent variable (Anxiety or Depression, respectively) using linear mixed effect model, where a random intercept will be included to account for repeated measurements from the same subject. We include in the model the following independent variables: the randomization arm, time and interaction between randomization arm and time, and baseline PROMIS Anxiety or PROMIS Depression T scores. Key biologic variables such as age, sex, TBI severity, and co-morbidities will be among some of the factors explored as potential confounders. Differences between treatment arms can then be obtained by estimating and testing the corresponding parameters in the linear mixed effect model.

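### The mixed model in 9.4.2 and 9.4.3 has only a random intercept: if correlation between surveys fades, its arm-by-time test rejects too often, and so does its day-180 contrast when only surveys to day 180 enter

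*Combined protocol and SAP*

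**What the plan says.** Section 9.4.1 sets the general rule: "For inferential tests, a two group t-test with a 0.05 two-sided significance level will be used". Section 9.4.2 first states "Change from baseline to 6-months post-intervention will be compared between the two arms". It then adds that the analysts will "model the dependent variable (Caregiver Strain) using linear mixed effect model, where a random intercept will be" included, with these fixed effects: "the randomization arm, time and interaction between randomization arm and time, and baseline Caregiver Strain T scores". It closes: "Differences between treatment arms can then be obtained by estimating and testing the corresponding parameters in the linear mixed effect model". Section 9.4.3 repeats the approach for anxiety and depression, again with a "linear mixed effect model, where a random intercept will be included to account for repeated measurements from the same subject".

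Neither section mentions a random slope, serial correlation, an unstructured covariance or robust standard errors. Neither says whether time is linear or categorical, which surveys enter, or which parameter is the test. Surveys are due "at the end of each month (day 30, 60, 90, 120, 150, 180") under 8.1.5.3 and again at "3-months (270 days) and +6-months (360 days) follow-up" under 8.1.5.4, so six or eight post-baseline surveys could enter. The only planning correlation, in the exploratory part of 9.2, is exchangeable, from 0.4 to 0.8. Sections 1.1, 3 and 4.2 put the primary assessment at the end of the 180-day period, and I take day 180 as the time point of interest.

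**The concern.** A random intercept makes day 30 correlate with day 60 exactly as it does with day 180 or day 360, and gives every survey the same variance once baseline is adjusted for. If correlation really weakens as the gap grows, two things go wrong.

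- Differences between distant surveys vary more than the model believes. This affects any arm-by-time test.
- Baseline predicts late surveys less well than early ones, so the variance left after baseline adjustment grows with time while the model pools it. This affects a contrast at a late visit such as day 180.

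In both cases the standard error can be too small and the test can reject too often. The same model serves the primary and both secondary endpoints.

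**Working it through.** **The plan's own figure.** The only figure stated for the primary endpoint concerns the t-test: 2 × (1.96 + 0.8416)² × 9.66² / 4.0² = 91.6, so 92 per arm, as in 9.2. The documents state no error rate for the mixed model, so it has to be derived.

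**Inputs.** From the documents: two-sided 5%; surveys at months 1-6, then 9 and 12; 140 per arm less 15% attrition = 119; SD 10 (T metric). Assumed: no arm effect, constant variance, and correlation at a gap of d months r(d) = r(1) × [r(6)/r(1)]^((d−1)/5).

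**Formulas.** With k surveys and a common baseline slope b (the mean of the k correlations with baseline), let R be the true covariance of score minus b × baseline. Let J be the k × k matrix with every entry 1/k. The random-intercept model replaces R by M = v_W (I − J) + v_B J, where v_W = tr[(I − J)R]/(k − 1) and v_B = tr(JR). For a contrast with weights c, the model variance is (2/n) c′Mc, the true variance is (2/n) c′Rc, and the rejection rate is 2Φ(−1.96 √(c′Mc / c′Rc)). The ratio does not depend on n.

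**One case in full: 0.8 falling to 0.5, six surveys, categorical time.**

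- Correlations with baseline: 0.800, 0.728, 0.663, 0.603, 0.549, 0.500; b = 0.641.
- Residual variance 100 × (1 − 2b·r + b²) by month: 38.5, 47.7, 56.1, 63.7, 70.7, 77.0. The model pools these to their mean, 59.0.
- Day-180 contrast: model SE √(2 × 59.0/119) = 0.995; true SE √(2 × 77.0/119) = 1.137.
- 1.96 × 0.995/1.137 = 1.715, a rejection rate of 8.6%.

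With eight surveys the pooled variance is 68.3 against 75.4 at day 180. The SEs are 1.071 and 1.126, and the rate is 6.2%.

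**All cases** (rejection %, six surveys / eight surveys):

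| Correlation, 1 to 6 months | Linear arm-by-time slope | Categorical, day 180 vs day 30 | Categorical day-180 contrast | Linear day-180 contrast |
|---|---|---|---|---|
| 0.8 to 0.6 | 14.6 / 21.6 | 10.0 / 6.1 | 8.1 / 6.0 | 11.5 / 5.8 |
| 0.8 to 0.5 | 17.8 / 23.8 | 11.6 / 6.6 | 8.6 / 6.2 | 13.1 / 5.8 |
| 0.8 to 0.4 | 20.3 / 24.6 | 12.8 / 7.1 | 8.8 / 6.4 | 14.1 / 5.6 |
| 0.8 to 0.75 | 7.8 / 12.0 | 6.5 / 5.3 | 6.1 / 5.3 | 7.3 / 5.4 |

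Under exchangeable correlation M equals R and every entry is 5.0.

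**Why eight surveys protect the day-180 contrast.** The mean survey time is (1+2+3+4+5+6+9+12)/8 = 5.25 months, close to month 6, so the linear day-180 contrast hardly uses the slope. Under categorical time, the later surveys pull the pooled variance up towards the day-180 value.

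**Simulation check.** REML fits, 2,000 null trials per setting, 120 per arm, 0% or 15% dropout unrelated to outcome. With correlation 0.8 per month of gap (0.8 to the power of the gap) and no dropout, the rates were:

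| Test | Six surveys | Eight surveys |
|---|---|---|
| Linear slope | 21.2% | 24.0% |
| Linear day 180 | 14.6% | 5.4% |
| Categorical joint arm-by-visit | 8.4% | 8.6% |
| Categorical day 180 | 8.8% | 6.7% |

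Across all settings, cluster-robust standard errors gave 3.6-6.3% and the t-test on change gave 4.0-5.9%. With exchangeable correlation (0.6), the random-intercept model itself gave 4.4-5.8%.

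**The case against.** A reader might infer that the day-180 test is inflated however time is coded. That does not hold. With all eight surveys it is close to nominal under either coding (5.6-6.4% in the strong-fading cases), and linear time does not make it worse than categorical time. The plan does not say which surveys enter, but its one repeated-measures count, in the exploratory sizing of 9.2, is eight post-baseline. The badly inflated test is the linear arm-by-time slope, and the plan specifies neither linear time nor the slope as the test.

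A reader might also infer that the trial will make false claims of benefit on all three endpoints. The documents do not support that either. The t-test is the stated inferential test in 9.4.1 and the basis of sample size for all three endpoints, the mixed model is added to the comparison of change, and the t-test keeps its level.

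Fading correlation is itself an assumption. With milder fading (0.8 to 0.75) most rates are about 5-8%, with 12.0% for the eight-survey linear slope. Changing variance over time could move the day-180 result either way.

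All of this stands and limits the point. It does not remove it: 9.4.2 and 9.4.3 say that arm differences will be estimated and tested in this model, nothing ranks it below the t-test, and the choices that decide whether its error is negligible or several-fold are left open.

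**Conclusion.** The point holds in limited form. A random intercept alone is valid if correlation is exchangeable, and unsafe if correlation fades. Under fading from 0.8 at 1 month to 0.4-0.6 at 6 months with constant variance, the nominal 5% arm-by-time test rejects about 15-25% with linear time and about 6-13% for a categorical day-180 against day-30 term. The day-180 contrast is materially inflated only if the model stops at day 180 (about 8-9% categorical, 11-14% linear). The fading pattern and the constant variance are my assumptions, not findings from the documents. This is a weakness in the model-based tests of the primary and both secondary endpoints and should be corrected; it does not invalidate the t-test comparison.

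**What to change.** In 9.4.2 and 9.4.3, model the post-baseline scores with categorical visit, arm-by-visit and the baseline score, preferably baseline-by-visit. Use an unstructured within-person covariance, or keep the random intercept and use cluster-robust standard errors. State which surveys enter, and name the day-180 arm contrast as the model-based test.

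The cost is SAP wording and more covariance parameters: with eight surveys, 8 × 9/2 = 36 in place of 2, which about 238 participants (2 × 119) can support. Cluster-robust errors add no covariance parameters. Site adjustment and Kenward-Roger degrees of freedom are optional and are not needed to cure this defect.

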4 STUDY DESIGN

4.1 OVERALL DESIGN

Study Design: This behavioral trial will use a two-arm randomized controlled design. Each of the up to 280 care partner participants will be randomized to an active “JITAI” arm or to a control arm. The random allocation of participants to the treatment arm or control arm establishes the basis for testing the statistical significance or difference between the groups in HRQOL (caregiver strain, depression and anxiety).

Randomization: Blocked randomization will be used to limit bias and achieve an equal distribution of participants to the control and treatment arms. A randomization list will be generated for each site and the study statistician will oversee randomization. The participant will be randomized once he/she is deemed eligible and has provided informed consent (i.e. at Enrollment prior to baseline data collection). The study coordinator/research assistant who consented the participant will use their site’s randomization list to assign the participant to the correct study arm.

Duration of Study Participation: Study participation for both arms of the study (control and JITAI) involves a baseline assessment, followed by an approximate 10-day run-in period then a 6-month (180 day) home monitoring period (in which the intervention will be administered to the JITAI group). After the completion of the 6-month (180 day) home monitoring period, post-intervention surveys will be administered at 3 months (90 days) and 6 months (180 days) after the end of the 6-month (180 day) home monitoring period. Thus, the total duration of the study is ~375 days.

Study Sites: This is a multi-site study involving two sites: University of Michigan and Baylor College of Medicine. University of Michigan is the lead site and their IRBMED will serve as the single IRB for this study.

Study Intervention: The just in time adaptive intervention (JITAI) uses sensor data derived from the Fitbit® (e.g., accelerometer-based estimates of physical activity and sleep) and real-time self-report ratings (assessed once daily) of HRQOL (caregiver strain, depression, anxiety) to deliver personalized “pushes” to participants via a study specific app (CareQOL app). The personalized pushes will be delivered on ~50% of the days over the 6-month intervention period.

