9.4.4 BASELINE DESCRIPTIVE STATISTICS

Care partners in each study group (JITAI and control) will be compared descriptively according to Consolidated Standards of Reporting Trials Guidelines.³⁵

T tests/ANOVA will be used to examine group differences for continuous variables (e.g., age, HRQOL outcomes, time since injury, functional status of person with TBI). Chi-squared/Fisher exact tests will be used to examine group differences for categorical variables (e.g., sex, ethnicity, race, education, marital status, relationship to person with TBI, TBI severity).

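### The primary and secondary models omit site although randomisation is listed by site, and leave the other adjustment covariates open; fixing both is a free improvement

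*Combined protocol and SAP*

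**What the plan says.** Section 9.4.2 (primary endpoint) compares change between arms and, in addition, fits a linear mixed model with a random intercept. Its listed terms are "the randomization arm, time and interaction between randomization arm and time, and baseline Caregiver Strain T scores". Then follows "Key biologic variables such as age, sex, TBI severity, and co-morbidities will be among some of the factors explored as potential confounders", and directly after it "Differences between treatment arms can then be obtained by estimating and testing the corresponding parameters in the linear mixed effect model". Section 9.4.3 repeats the structure for anxiety and depression; there too, age, sex, TBI severity and co-morbidities "will be among some of the factors explored as potential confounders". I find no inclusion rule, no date for fixing the covariates, and no statement of whether the model with or without them is the primary one.

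On allocation, Section 4.1 says "Blocked randomization will be used to limit bias and achieve an equal distribution of participants to the control and treatment arms" and "A randomization list will be generated for each site and the study statistician will oversee randomization". Site is therefore a stratification factor. The synopsis plans 120 participants at one site and 160 at the other. Site is neither a listed model term nor a named candidate covariate.

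Section 9.4.4 promises a descriptive comparison of the arms and also plans significance tests at baseline: "T tests/ANOVA will be used to examine group differences for continuous variables", with chi-squared or Fisher tests for categorical variables. It does not say that these tests feed the outcome model.

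**The concern.** There are two gaps in the same paragraph.

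The first is a mismatch between design and analysis. Blocking within site holds the arms close to balance at each site, so differences between sites largely drop out of the true sampling error of the arm comparison. A model without site still counts those differences as noise. The standard error is then too large, the test is conservative and power is lost.

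The second is that the adjustment set is open at both ends: the named variables are examples, and they are only some of those to be looked at. The stated motive is confounding, but baseline differences between randomised arms arise by chance; covariates belong in the model for precision. With an open list and no fit labelled as primary, a reader of the results cannot tell whether the reported model was the only one considered.

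**Working it through.** **1. The plan's own figure.** Section 9.2: difference 4.0, SD 9.66, two-sided 0.05, power 80%. n = 2 × (1.960 + 0.842)² × 9.66² / 4.0² = 2 × 7.85 × 93.3 / 16 = 91.6, so 92 per group, as stated. Nothing below changes it.

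**2. Omitting site.** Sites of 120 and 160 give p = 120/280 = 0.4286 and p(1 − p) = 0.2449. Let δ be the between-site difference in outcome SDs and σ² the within-site residual variance. With balance inside each site, the true variance of the arm difference depends on σ² alone, but a model without site estimates σ² + 0.2449δ². The standard error is too large by

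k = √(1 + 0.2449δ²/σ²).

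Type I error is 2Φ(−1.960k). If the test with site in the model has 80% power, power without site is Φ(2.802 − 1.960k). I use σ² = 1 (no baseline adjustment) and σ² = 1 − 0.6² = 0.64 (baseline score in the model, assumed baseline–outcome correlation 0.6).

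| δ (assumed) | k, σ² = 1 | Type I | Power | k, σ² = 0.64 | Type I | Power |
|---|---|---|---|---|---|---|
| 0 | 1.000 | 5.0% | 80.0% | 1.000 | 5.0% | 80.0% |
| 0.25 | 1.008 | 4.8% | 79.6% | 1.012 | 4.7% | 79.3% |
| 0.5 | 1.030 | 4.3% | 78.3% | 1.047 | 4.0% | 77.3% |
| 0.8 | 1.075 | 3.5% | 75.6% | 1.116 | 2.9% | 73.1% |

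Simulation (20,000 trials per setting, sites of 120 and 160) agrees. Without baseline adjustment, type I error was 5.1%, 4.9%, 4.3% and 3.4% at δ = 0, 0.25, 0.5 and 0.8. With baseline adjustment it was 5.1%, 3.9% and 2.9% at δ = 0, 0.5 and 0.8. With site in the model it stayed at 4.9–5.2% throughout.

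For scale, at SD 9.66 a δ of 0.5 is 0.5 × 9.66 = 4.8 points and a δ of 0.8 is 7.7 points, both larger than the 4.0-point target difference.

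**3. Open covariate choice.** Null trials with N = 280 × 0.85 = 238 (119 per arm; Section 9.2 states 15% attrition for its exploratory table). The baseline score was always included, with an assumed correlation of 0.6. Four independent covariates jointly explained an assumed 5%, 10% or 20% of outcome variance. I ran 4,000 trials per setting, so the Monte Carlo standard error near 5% is √(0.05 × 0.95/4000) = 0.3 points.

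| How covariates enter | 5% | 10% | 20% |
|---|---|---|---|
| All four, fixed in advance | 4.6% | 4.4% | 4.7% |
| Those imbalanced at p < 0.05 | 4.7% | 4.2% | 4.0% |
| Those imbalanced at p < 0.20 | 4.4% | 3.8% | 3.4% |
| Those associated with outcome, p < 0.05 | 4.6% | 4.5% | 4.7% |
| Smallest treatment p over all 16 subsets | 8.0% | 9.4% | 12.7% |

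Only the last row exceeds 5%. Selecting on imbalance, if anything, makes the test conservative.

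Both checks use a single-time-point model in place of the full mixed model. The direction carries over, since an omitted site effect goes into the random-intercept variance; the exact sizes would differ.

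**The case against.** The strongest reply is that the core analysis is already fixed. The four model terms are listed, Section 9.4.1 names a two-group t-test at two-sided 0.05, and the sample size rests on that test. On this reading the confounder sentence describes supplementary adjustment, and the gap is one of detail. Much of this stands. The text could mean supplementary work, but it does not say so, and the sentence on testing the arm effect follows directly. One added line would settle it.

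Three stronger readings are tempting, and the documents do not support them.

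- A reader might infer a stated data-driven rule, with the primary estimate chosen after results are seen. The text states no rule and no timing; it leaves the matter open.
- A reader might infer that the baseline tests in Section 9.4.4 select the covariates and so inflate error. No section makes that link, and the table shows that such selection would not inflate error.
- A reader might take the missing site term as a threat to validity. It works the other way: the test becomes conservative, and noticeably so only if the sites differ substantially, for which the documents offer no evidence.

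It is also fair to say that the documents do not show age, sex or TBI severity to be prognostic beyond the baseline score, so making them mandatory would be a preference.

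**Conclusion.** The concern holds as a mismatch between design and analysis plus an under-specified covariate set. It is not a demonstrated error-rate problem.

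Leaving out site costs nothing if the sites are alike. At an assumed 0.5 SD site difference, type I error is about 4% and the power loss is about 2 to 3 points. At 0.8 SD, type I error is about 3% and the loss is about 4 points without baseline adjustment or 7 with it. These losses are measured from 80% power and would be smaller where power starts higher.

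The open covariate list permits type I error of about 8–13% only under deliberate reporting of the most favourable of all subsets, with assumed covariate strengths. That range is a worst case and not a forecast. The case for fixing the list is that it removes the possibility and gives the adjustment its proper rationale, precision. The planned 92 per group is unaffected. I would class this as a free improvement.

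**What to change.** In Sections 9.4.2 and 9.4.3:

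- Add site as a fixed effect in the primary and secondary mixed models.
- Replace the confounder sentence with a covariate set fixed before any comparative data are seen: baseline score and site, plus age, sex and TBI severity if the sponsor wants them for precision. State that they enter whatever the baseline table shows.
- Label any other adjustment, including co-morbidities, as sensitivity analysis.

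Removing the baseline hypothesis tests from Section 9.4.4 and keeping the descriptive comparison is optional; it changes no primary result.

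The cost is a few lines of wording and one degree of freedom for site. No new data are needed and the sample size does not change. What is given up is freedom to choose covariates later.
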